7.2.5.3. Administrative status for medicinal product

The following will be recorded on the CRF for each patient:

- Treatment duration: Record start date and stop date (year/month/day) of the treatment of Xeljanz. If the medication is being continued at the completion of the study, record the start date only.
- Daily dose: Record single dose of Xeljanz in mg.
- Daily dosing frequency: Record dosing frequency per day.
- Reason for dose adjustment: If there are any dose adjustments during the study, record the reason(s).

7.2.5.4. Concomitant treatments

Any concomitant treatments should be recorded on the CRF for each patient. The information should include:

- Name of the drug: Record generic name of the concomitant medication.
- Daily dose: Record single dose and dosing frequency of the concomitant medication.
- Duration of the treatment: Record the start date and stop date (year/month/day) of the concomitant medication. If the medication is being continued at the completion of the study, record the start date only and check “ongoing”.
- Purpose of the treatment: Record purpose of the concomitant treatment in detail.

7.2.5.5. Safety and effectiveness data

Please refer to [Section 7.3](#) for safety and effectiveness assessment and data collection.

7.3. Variables

7.3.1. Safety variables

Safety will be assessed by the investigator based on all AEs that occur during the 24 weeks (52 weeks for the long-term users) from the first treatment for all patients who have received at least 1 dose of Xeljanz according to the local product document.

7.3.1.1. Adverse events

Please refer to [Section 9](#) for the definition of non-serious and serious adverse events (SAEs).

Any AEs observed and reported within the reporting period will be recorded on the CRF by the investigator, regardless of the causal relationship with Xeljanz (see [Section 9.2](#)). The AEs can be reported by the patients. The investigator will also collect AE data by asking the patient questions such as “Have you had any health problem since the last visit?”

Check either “yes” or “no” in the AE section of CRF. If “yes”, record the following information:

Event name: Record the name of the AE according to the MedDRA(Medical Dictionary for Regulatory Activities). If there is no appropriate term in the MedDRA, record the name of the AE according to the Medical Terminology Dictionary written by the Korean Medical Society. If possible, specify diagnosis, not individual symptoms.

Date of onset: Record the onset date of the AE. Record approximate date if an actual date is unknown.

Date of recovery: Record the stop date of the AE if the outcome of the AE is recovered or recovered with sequelae (see below). Record approximate date if an actual date is unknown.

Seriousness: Check either “yes” or “no” to indicate if the event is a SAE. If “yes” record appropriate category of the seriousness (see [Section 9](#)for the definition and reporting of SAEs).

Severity: Evaluation of AE severity must be done according to the following categories:

- **Mild**: Not causing any significant problem to the patient. Administration of medicinal product continues without dose adjustment.
- **Moderate**: Causes a problem that does not interfere significantly with usual activities or the clinical status. Dose of the medicinal product is adjusted or other therapy is added due to the AE.

- Severe: Causes a problem that interferes significantly with usual activities or the clinical status. The medicinal product is stopped due to the AE.

If the severity of an AE changes, the AE must be entered separately. Record the stop date of the previous severity and onset date of the new severity – along with completion of all other related items.

Causality assessment: The causal relationship of AEs to the medicinal product must be allocated by the investigator according to the following criteria in alignment with the requirements of MFDS:

- Certain
 - It follows a reasonable time sequence from administration of the drug (before and after the study medication);
 - It could not be explained by other drugs, chemical substances or accompanying diseases;
 - It has clinically reasonable reaction on cessation of the drug;
 - It has pharmacological or phenomenological reaction to re-administration of the drug, where necessary.
- Probable/likely
 - It follows a reasonable time sequence from administration of the drug (before and after the study medication);
 - It could not be explained by other drugs, chemical substances or accompanying diseases;
 - It has clinically reasonable reaction on cessation of the drug (no information on re-administration).
- Possible
 - It follows a reasonable time sequence from administration of the drug;
 - It could also be explained by other drugs, chemical substances or accompanying diseases;
 - It lacks information or has unclear information on discontinuation of the drug.
- Unlikely

- It is not likely to have a reasonable causal relationship from administration of the drug. Rather, it seems to be temporary;
- It could also be reasonably explained by other drugs, chemical substances or latent diseases.
- Conditional/unclassified
 - It needs more data to make an appropriate assessment or its additional data are being reviewed.
- Unassessable/unclassifiable
 - Lack of sufficient information or conflicting information hampers accurate causality assessment or supplementation or confirmation.
- Not applicable
 - Causality is assessed but does not fall into any categories

All AEs, except for those with a causality of “unlikely”, are considered as AEs whose causal relationship to the study drug can not be excluded (ie, adverse drug reaction [ADR]).

Action taken: With regard to the medicinal product, actions will include:

- Permanently discontinued;
- Temporarily discontinued or delayed;
- Dose reduced;
- Dose increased;
- No change;
- Not applicable.

Outcome: Evaluation of outcome will include:

- Recovered;
- Recovered with sequelae;
- Recovering;
- Not recovered;

- Unknown.

Please refer to [Section 9](#) for the requirements for reporting safety events to Pfizer Safety during the study.

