## 6.2. Safety Analyses

Safety analyses will be performed based on data of safety analysis set. All adverse events in CRF will be classified by SOC and PT according to the latest version of MedDRA.

- 1) All adverse events investigated after administration of Xeljanz® during the study will be summarized with the number of subjects having adverse events, incidence of adverse events with 95% confidence interval (C.I) and the number of adverse events by categorizing as follows:
  - Serious adverse events and serious adverse drug reactions
  - Unexpected serious adverse events and unexpected serious adverse drug reactions
  - Unexpected adverse events and unexpected adverse drug reactions
  - Adverse events and adverse drug reactions
  - Adverse events of safety concerns\*

\*Adverse event with important identified risks and important potential risks in relation to the safety specification under the risk management plan

- 2) All adverse events investigated after administration of Xeljanz® during the study will be summarized with the frequency and percentage of adverse events by categorizing as follows:
  - Occurrence status of adverse events by their severity
    - Mild
    - Moderate
    - Severe
  - Occurrence status of adverse events by their outcome
    - Recovered
    - Recovered with sequelae
    - Recovering
    - Not recovered
    - Unknown

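### Each change in AE severity creates a new CRF entry, and SAP 6.2 has no rule joining the entries of one episode, so its event counts and event-level tables can count one AE several times

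*Protocol*

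**What the plan says.** Protocol 7.3.1.1 makes splitting mandatory: "If the severity of an AE changes, the AE must be entered separately". The investigator is then told: "Record the stop date of the previous severity and onset date of the new severity", "along with completion of all other related items". Each segment is therefore a full record with its own seriousness, causality, action and outcome.

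The same section says of the recovery date: "Record the stop date of the AE if the outcome of the AE is recovered or recovered with sequelae". Its outcome list has five categories: recovered, recovered with sequelae, recovering, not recovered and unknown. None stands for an AE that continues at another grade.

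SAP 6.2 starts from the whole CRF: "All adverse events in CRF will be classified by SOC and PT". Under item 1, AEs are "summarized with the number of subjects having adverse events, incidence of adverse events with 95% confidence interval (C.I) and the number of adverse events", separately for serious, unexpected serious, unexpected, all, and risk-management-plan safety-concern events. Under item 2 they are "summarized with the frequency and percentage of adverse events by categorizing as follows", the categories being severity, outcome, seriousness, action taken and causality. SAP 6.2 item 6 repeats the event counts for patients excluded from the safety set, and SAP 6.4 repeats items 1 to 4 for long-term users.

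Neither document links segments, takes the worst grade, or takes the last outcome.

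**The concern.** The data-entry rule and the analysis rule use different units. The protocol creates one record per grade of an AE; the SAP reports events and percentages of events without saying what one event is. An AE that goes from mild to moderate and back to mild gives three records. A serious AE that changes grade while still marked serious adds a second entry to the serious-event count.

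The situation is not contrived. Protocol 7.3.1.1 ties grades partly to what is done with the drug: moderate includes added therapy, severe includes stopping the product. An AE handled first in one way and then in the other changes grade under those definitions and has to be re-entered.

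At stake are the number-of-events column for every class of AE and all the item 2 tables. The SAP plans no subject-level version of the item 2 tables, so nothing in the report would correct them. Two programmers working from the same database could produce different safety tables and both claim to follow the SAP.

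**Working it through.** The documents state no figure on this point, so there is none to reproduce. The check is a counting identity on assumed values.

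**Inputs**
- From Protocol 7.3.1.1: one new record per severity change.
- From SAP 6.2: events counted from all AEs in the CRF, with no linking step.
- Assumed: E = 100 true AEs, R = 70 finally recovered, S = 10 severe at worst grade.
- Assumed: a share q of AEs changes grade exactly once, with q from 5% to 30%.

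**Formulas**
- Records = E(1 + q).
- Recovered share, superseded segments coded recovered: (R + Eq) / [E(1 + q)].
- Recovered share, superseded segments coded recovering or not recovered: R / [E(1 + q)].
- Severe share: S / [E(1 + q)]. With one change per AE, the extra record is always below that AE's worst grade, so it is never severe.

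**Results**

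| q | Records | Recovered, if coded recovered | Recovered, if coded recovering or not recovered | Severe |
|---|---|---|---|---|
| one record per AE | 100 | 70% | 70% | 10% |
| 5% | 105 | 71.4% | 66.7% | 9.5% |
| 10% | 110 | 72.7% | 63.6% | 9.1% |
| 20% | 120 | 75.0% | 58.3% | 8.3% |
| 30% | 130 | 76.9% | 53.8% | 7.7% |

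At q = 20%: (70 + 20)/120 = 75.0%, 70/120 = 58.3% and 10/120 = 8.3%.

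Mixed coding falls between the two recovered columns. If 70% of the superseded segments were coded recovered, the table would show (70 + 14)/120 = 70%, the true value. Both the sign and the size of the error therefore depend on coding that the documents do not fix.

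**Subject level.** A patient with two segments of one AE is still one patient with an AE. In a simulated example (600 patients, 30% chance of an AE, 20% of AEs split), 176 subjects had an AE under either count, while there were 217 records for 176 true events. Incidence by subject and its confidence interval do not depend on q.

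**The case against.** The strongest case on the other side has four parts.

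1. *The SAP never says that a record is an event.* This is correct. The counting unit is undefined, and neither the dummy tables of SAP Attachment 1 nor the eCRF is in the available text; either might link segments. A reader might infer that the SAP expressly counts records as events, but that is only its literal reading. The objection does not remove the problem: a mandatory splitting rule next to an undefined unit is itself the gap.

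2. *False recoveries are not shown.* A reader might infer that every superseded segment, because it needs a stop date, enters the outcome table as recovered and biases it upwards. The protocol does not support this. Its date rule runs from outcome to date, not from date to outcome; the stop date of a severity is the end of a segment; and an investigator may choose recovering, not recovered or unknown. For an AE that worsens, not recovered would be a natural choice. This part stands in full: distortion is established, its direction is not.

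3. *The primary result is safe.* Protocol 7.7.1 names the incidence of AEs as the primary interest. Counted by subject, incidence does not move, nor do the subgroup tests and logistic regression of SAP 6.2 items 3 and 4. This stands and limits the point to event counts and descriptive tables.

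4. *The size is assumed.* This also stands. The documents give no rate of severity change, and grades tied to drug action make the rate hard to guess.

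**Conclusion.** The point holds for event-level output only. Read literally, Protocol 7.3.1.1 and SAP 6.2 together count one continuing AE two or more times. Event counts, including those of serious, unexpected and safety-concern events, rise by the share of AEs that change grade: 1.1 to 1.3 times at an assumed 10% to 30% with one change each. Compared with a worst-grade tabulation, the severity mix is diluted by lower-grade segments; an assumed 10% severe falls to between 9.1% and 7.7% over that range. Outcome percentages can move either way. The seriousness, action and causality tables share the same undefined denominator.

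The documents do not support a claim that the study's incidence estimate is inflated, or that recovery is systematically overstated. The correction is worth making because safety is the primary endpoint, these tables are the only planned description of AE severity and outcome, and no new data are needed.

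**What to change.** Add an episode rule to SAP 6.2, and state that it also applies to SAP 6.4 and to the excluded population (SAP 3.5 and 6.2 item 6):

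- Consecutive records of the same preferred term in the same patient that arise from a severity change are one event. A new occurrence after recovery remains a separate event.
- Link them with a small date tolerance or by manual review. Exact matching of onset to previous stop is fragile, because Protocol 7.3.1.1 allows approximate dates.
- Count the event once, at maximum severity, with the final segment's outcome, the worst seriousness, the strongest action taken and the closest causality. State the ranking used for action and causality.
- Do not tabulate the outcome of superseded segments. Keep all segments in a listing.

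The cost is a short paragraph in the SAP, a short derivation step with some manual review, and slightly lower event counts. Data collection and the subject-level analyses stay as they are.

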## **Statistical Analysis Plan for rPMS**

- Occurrence status of adverse events by their seriousness [SAE]
  - Results in death
  - Is life-threatening
  - Requires inpatient hospitalization or prolongation of hospitalization
  - Results in persistent or significant disability/incapacity
  - Results in congenital anomaly/birth defect
  - Other important medical event
- [Non-SAE]
- Occurrence status of adverse events by action taken
  - Permanently discontinued
  - Temporary discontinued or delayed
  - Dose reduced
  - Dose increased
  - No change
  - Not applicable
- Occurrence status of adverse events by their causality assessment to Xeljanz®
  - Related to Xeljanz®: ① Certain  
② Probable/likely  
③ Possible  
⑤ Conditional/unclassified  
⑥ Unassessable/unclassifiable  
⑦ Not applicable
  - Not related to Xeljanz®: ④ Unlikely
- Occurrence status of adverse events by their other causality assessment (In case of 'Unlikely')
  - Disease under the study
  - Other diseases
  - Concomitant treatment-medication or non-medication
  - Other

3) Occurrence status of adverse events by demographic and other baseline characteristics

- The incidence of adverse events and 95% C.I will be presented by categorical variables of demographic and other baseline characteristics.
- To identify statistically significant difference in the incidence of adverse events by categorical variables of demographic and other baseline characteristics, Chi-square test ( $\chi^2$  test) or Fisher's exact test (if the expected frequency for each cell under 5 is more than 20%) will be performed.

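### The AE outcome list and the matching SAP outcome table have no fatal category, so a fatal AE sits among unresolved or unknown outcomes and cannot agree with the death row of the seriousness table

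*Protocol*

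**What the plan says.** **Outcome field.** Protocol 7.3.1.1 opens the item with "Outcome: Evaluation of outcome will include" and names five categories: Recovered, Recovered with sequelae, Recovering, Not recovered and Unknown.

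**Outcome table.** SAP 6.2 item 2, under "Occurrence status of adverse events by their outcome", has the same five rows. The unit is the adverse event, not the patient.

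**End date.** Protocol 7.3.1.1 asks for one conditionally: "Date of recovery: Record the stop date of the AE if the outcome of the AE is recovered or recovered with sequelae". The only other AE stop date arises when severity changes: "Record the stop date of the previous severity and onset date of the new severity".

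**Seriousness.** For an SAE the investigator must also "record appropriate category of the seriousness". Death is the first criterion in protocol 9.4.2, and the seriousness table in SAP 6.2 item 2 has the row "Results in death".

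**Expedited reporting.** Protocol 9.1 requires immediate notification of fatal SAEs to the sponsor, applies the same timeframe to follow-up information, and asks for available autopsy findings after a death.

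**Non-completion.** Protocol 7.2.5.1 offers three reasons: AE, lack of effectiveness, or others.

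**The concern.** Safety is the primary endpoint, and the outcome table is one of its planned displays in a report to the regulator. A reader expects such a table to separate events that ended in death from events still open at last contact. As planned, it cannot. A fatal infection and a persisting mild rash could share the Not recovered row.

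The same report will also contain a seriousness table that does show deaths. If any death occurs, one table reports a fatal AE and the other reports none, and the plan does not link the two. What is at stake is the accuracy and internal consistency of one safety table, not a planned estimate.

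**Working it through.** There is no figure to reproduce, so the check compares the passages and works by elimination.

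**Step 1. Is the omission in both documents?** Yes. The protocol and SAP lists match category for category. Two identical lists make it unlikely that a sixth item was lost when the text was extracted.

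**Step 2. Where can a fatal AE go in the outcome field?**

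| Category | Can it hold a fatal AE? | What else it holds |
|---|---|---|
| Recovered | No | Resolved events |
| Recovered with sequelae | No | Resolved events with lasting effects |
| Recovering | No | Improving events |
| Not recovered | Yes, by default | Unresolved non-fatal events |
| Unknown | Yes, by default | Events with no outcome information |

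Only the last two remain, and both also hold non-fatal events. The outcome table alone therefore cannot show the number of fatal AEs.

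**Step 3. Does the end date identify them?** No. It is tied to the two recovered categories, and the severity-change stop date closes a severity episode rather than a fatal event. No date of death is named among the CRF items the protocol describes, and death is not a listed reason for non-completion.

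**Step 4. Is the death recorded elsewhere?** Yes. The seriousness category is a separate CRF item, death is one of its values, and the SAP tabulates it. Fatal SAEs also reach the sponsor's safety group on a separate report form.

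**Step 5. Do the two tables agree?** Suppose *d* AEs are fatal and are coded as such under seriousness. The seriousness table then shows *d* in its death row. The outcome table shows no fatal events, and those *d* events are spread over Not recovered and Unknown. The tables disagree whenever *d* is at least 1. Neither the data management section (protocol 7.6) nor the SAP describes a reconciliation between the fields or with the SAE reports.

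**The case against.** The strongest reply is that deaths are captured and displayed. The seriousness criterion records them, the SAP gives them a row, and fatal SAEs are notified at once with follow-up. That stands, and it limits the point to the outcome field and table. A reader might infer that deaths go uncounted; the documents do not support that.

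A reader might also infer that time to death or case fatality for infections, tuberculosis or cancer becomes impossible to analyse. Neither document plans such an analysis. A fatal row would not supply case fatality by event type anyway, because the outcome table is not specified by type.

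A third tempting reading is that no date of death is collected anywhere. The CRF and the safety report form are not among the documents, and the protocol's wording introducing the list could be non-exhaustive. All that can be said is that no such date is named among the CRF items described.

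It may also be argued that an SAE entered as a hospitalization could later prove fatal without being recoded. The protocol does not spell out updating of the seriousness category, but it requires the outcome to be pursued and follow-up to be reported, and nothing fixes the category at first entry or limits it to one. That scenario is a reason to reconcile, not evidence of lost deaths.

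Finally, a new CRF code is hard to add late. Data collection was planned to end on 19 September 2022, and SAP version 1.1 is dated 2 November 2022. That also stands, and it is why the fix includes a derivation from data already held.

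**Conclusion.** The point holds in a narrow form. The outcome list in protocol 7.3.1.1 and the outcome table in SAP 6.2 item 2 cannot show a fatal AE. Followed as written, they place it with unresolved or unknown events and out of step with the seriousness table.

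The size is one misplaced record per fatal AE. The documents give no death rate, so no expected count can be stated. Expressing one death as a share of patients would not measure the error, because this table counts events. AE incidence with its confidence interval, the count of fatal AEs under seriousness, and the analysis sets are all unchanged.

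The conclusion assumes that the CRF uses the five listed outcomes and that the SAP table is produced with the rows it names. If the CRF already carries a fatal code, only the SAP row is missing.

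**What to change.** Add Fatal to the outcome list in protocol 7.3.1.1 and as a row of the outcome table in SAP 6.2 item 2.

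Where data collection has ended, derive the category instead of returning to the sites. Set the outcome to Fatal for AEs whose seriousness category is death, and check these against the SAE reports in both directions. Take the date of death from those reports where they hold it. Before database lock, reconcile the fatal row of the outcome table with the death row of the seriousness table, and explain any remaining difference in a footnote.

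The cost is one table row, one derivation rule and a short check of the few fatal SAE reports. No endpoint, test, analysis set or clinical rule changes.
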